6.9.1 Imputation Rules for Incomplete Dates

As a general principle, no imputation of missing data will be done. Exceptions are the start and stop dates of AEs and concomitant medication. The imputed dates will be used to allocate the concomitant medication and AEs to Treatment Visit and to determine whether an AE is/is not treatment emergent. Listings of the AEs and concomitant medications will present the actual partial dates; imputed dates will not be shown.

In case of missing partial start and stop dates for AEs and concomitant medications, the following rules will be used:

If the start date is missing or partial:

- if the month is missing, use January
- if the day is missing, use the first day of the month under consideration
- if the year is missing, use year of the informed consent date
- if the entire date is missing, use informed consent date

If the stop date is missing or partial:

- if the month is missing, use December
- if the day is missing, use the last day of the month under consideration
- if the year or the entire date is missing, set the stop date to December 31st, 2019

If the imputed start date is after the stop date, then the imputed start date will be 1 day prior to the stop date.

For AEs, a missing or incomplete onset date will be imputed according to the following conventions.

If an onset date is missing or only the year is known, the imputed onset date will be the date of first dose of study drug.

If only the year is known for the AE onset date, the imputed onset date will be the latest of the following non-missing dates:

- Date of first dose of study drug
- January 1 of the year of AE onset date

If only the month and year is known for the onset date, set the surrogate onset date to the first day of that month and then apply the following rules.

- If the month and year of the onset date is prior to the month and year of the first dose of study drug, then the surrogate onset date will be the imputed onset date.
- If the month and year of the onset date is on or after the month and year of the first dose of study drug, then the imputed onset date will be the latest of the following non-missing dates:
 - Date of first dose of study drug
 - Surrogate onset date

If the imputed onset date is after the adverse event end date, the imputed onset date will be the same as the adverse event end date.

If more than one observation exists within the analysis window, the observation closest to the scheduled visit day will be selected for that visit. If there are two observations that have the same distance from the scheduled day, the value that is after the scheduled day will be selected in the analysis. If more than one observation is made on the same day, an average value if continuous or the worst value if categorical will be included in the analysis.

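### SAP 6.9.1 gives two unranked sets of imputation rules for AE onset, and for some incomplete dates they give opposite treatment-emergent status

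*SAP*

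**What the plan says.** SAP 6.9.1 states that imputed dates are used, among other things, "to determine whether an AE is/is not treatment emergent". It then gives two blocks of rules.

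**General block.** It opens: "In case of missing partial start and stop dates for AEs and concomitant medications, the following rules will be used". For start dates it says "if the month is missing, use January"; "if the day is missing, use the first day of the month under consideration"; and "if the entire date is missing, use informed consent date". A missing year takes the year of consent. A start date imputed later than the stop date is moved to the day before the stop date.

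**AE block.** It opens: "For AEs, a missing or incomplete onset date will be imputed according to the following conventions". Its first rule is: "If an onset date is missing or only the year is known, the imputed onset date will be the date of first dose". Its second is: "If only the year is known for the AE onset date, the imputed onset date will be the latest of the following non-missing dates", the candidates being first dose and 1 January of the onset year. When month and year are known, an onset month before the first-dose month gives the 1st of the onset month; otherwise the later of first dose and that 1st is used. An onset imputed later than the end date is set to the end date.

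Nothing in the section ranks the two blocks. Protocol 7.9 says that AE and medication dates will be imputed but gives no rule that would settle the matter. Under SAP 6.5.1 an AE is treatment emergent from the start of study drug to 30 days after EOT, and the summary tables are based on TEAEs.

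**The concern.** Both blocks cover AE start dates by their own terms, so a programmer who follows the SAP literally can take either. The general block can put an onset on the consent date, on 1 January or on the 1st of the month, all of which may precede first dose. The AE block mostly pulls the same event to first dose or later. Because the imputed date determines treatment-emergent status, the choice decides whether the event appears in the TEAE tables.

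Safety is the first-listed objective and the sample is small. With about 30 subjects, one subject moving in or out of a TEAE row changes its incidence by 1/30 = 3.3 percentage points; in an age cohort at the targeted minimum of 5 evaluable subjects the change is 1/5 = 20 points. The listings show the partial dates but not the imputed ones, so a reader could not see directly which rule had been used.

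**Working it through.** The plan states no figure to reproduce. The check is to apply each block literally and compare the results.

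**Inputs.** The rules are those of SAP 6.9.1. Screening runs from day -5 to day 1 pre-dose (SAP 2.2), so consent is taken as 0 to 5 days before first dose. The TEAE window is from SAP 6.5.1. AEs are collected from consent to 60 days after the last dose (Protocol 5.5.1). An onset imputed to the first-dose date is counted as treatment emergent. Stop dates are left out.

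**One subject.** Assume consent on 9 June 2019 and first dose on 12 June 2019.

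| Recorded onset | General block | AE block | Status differs? |
|---|---|---|---|
| Nothing | 9 Jun 2019 | 12 Jun 2019 | Yes |
| 2019 | 1 Jan 2019 | 12 Jun 2019 | Yes |
| Jun 2019 | 1 Jun 2019 | 12 Jun 2019 | Yes |
| May 2019 | 1 May 2019 | 1 May 2019 | No |
| Jul 2019 | 1 Jul 2019 | 1 Jul 2019 | No |
| 2020, later-of rule | 1 Jan 2020 | 1 Jan 2020 | No |

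**All start days.** The same comparison was run over 365 assumed first-dose dates from 1 March 2019, each with a consent lag of 0 to 5 days (365 × 6 = 2,190 combinations). It asked only whether the imputed onset fell before first dose.

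- Fully missing: the blocks disagree in 365 of 365 at each lag from 1 to 5 days, and in 0 of 365 at lag 0, where consent and first dose share a date.
- Year only, first-dose year: 2,184/2,190 = 99.7%. The exception is first dose on 1 January.
- Year only, earlier year: 2,190/2,190 = 100%.
- Month and year equal to the first-dose month: 2,118/2,190 = 96.7%. The exceptions are the 12 first-dose dates that fall on the 1st (12 × 6 = 72 combinations).
- Month and year in the month before or after, or year only in the following year: 0%.

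These percentages are shares of calendar start dates within a pattern. They are not shares of AEs.

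**The two year-only rules in the AE block.** They give different dates only when the onset year is later than the first-dose year. Both dates are then on or after first dose, so status can differ only at the far end of the TEAE window. Assume first dose on 1 October 2019 and last dose on 20 November 2019. The window closes on 20 November + 30 days = 20 December 2019; collection closes on 20 November + 60 days = 19 January 2020. For an onset recorded as 2020, the first rule gives 1 October 2019 (treatment emergent). The second gives 1 January 2020, 42 days after the last dose (not treatment emergent). Within the 60-day collection period, this needs 1 January to fall 31 to 60 days after the last dose, that is, a last dose from 2 November to 1 December.

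**The tie-breaks.** If an onset imputed to first dose is later than the end date, the end date is itself before first dose. The end date and the day before it are then both pre-dose, so the difference between the tie-breaks essentially never changes treatment-emergent status.

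**The case against.** The best reply is that a specific rule placed after a general one normally overrides it. Read that way, the AE block governs AE onset, and fully missing and first-dose-month onsets go to first dose, the conservative choice for TEAEs. Harm would need someone to apply the general block and ignore the AE block. This is a natural reading, but the SAP does not state it, the general block names AEs expressly, and it leaves the year-only contradiction inside the AE block untouched.

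A reader might infer that any AE with a missing or partial onset changes status. That does not follow: the blocks agree for month/year onsets outside the first-dose month, for year-only onsets in a later year under the later-of rule, and for fully missing onsets when consent and first dose share a date.

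A reader might also infer that the safety result is understated. The documents do not support that either. They give no count of incomplete onset dates; eCRF entry is expected within 5 days of each visit (Protocol 8.1); and all AEs stay in the listings with their actual partial dates. Nor are the affected events known to be on treatment. Collection starts at consent, so some may truly be pre-dose, and a recorded year before the first-dose year shows that the onset was.

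**Conclusion.** The contradiction is real but limited. The two blocks give opposite treatment-emergent status for (a) a fully missing onset when consent is before the first-dose date; (b) a year-only onset in or before the first-dose year, unless first dose is 1 January of that year; and (c) a month/year onset equal to the first-dose month, unless first dose is on the 1st. If the general block were applied to AE onset, events in (a) to (c) would leave the TEAE tables and remain only in the listings. Separately, the AE block's two year-only rules can disagree on status when 1 January is more than 30 days after the last dose.

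The number of affected events cannot be computed, so no bias in the safety results is shown. The conclusion rests on a literal reading of both blocks and on counting a first-dose-date onset as treatment emergent. It matters because two programmers following the same SAP could produce different TEAE tables.

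**What to change.** In SAP 6.9.1:

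1. State that for AE onset dates the AE-specific conventions take precedence over the general start-date rules wherever they apply. Any remaining partial pattern (for example month known but year missing, or day and year known but month missing) is imputed no earlier than first dose unless the known parts show a pre-dose onset. A precedence sentence is safer than removing AEs from the general block, which would leave these patterns without a rule.
2. Delete the year-only clause from the first AE-specific rule, so that year-only onsets use the later of first dose and 1 January. While editing, the sponsor could consider the same known-parts exception for a year-only onset before the first-dose year, which the later-of rule would otherwise move to first dose.
3. Use the end-date tie-break for AEs, and keep the one-day-prior tie-break for concomitant medications only, which would otherwise have none.

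The cost is a few sentences and no new data. Any date derivation already programmed would need checking; the documents do not show whether one exists. Protocol 7 requires the SAP to be final by database soft lock, and the edit should be made before then so that the choice of rule cannot follow the data.

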5.4 Safety Assessment

5.4.1 Vital Signs

Vital signs (temperature, pulse rate and blood pressure) are to be measured within 1 hour before the start and approximately 1 hour after the end of each infusion on dosing days. No additional vital signs are needed on dosing days for oral administration. Temperature to be taken as per institution's policy based on age of subject. Vital signs will be collected as shown in the schedule of assessments [Table 1 and Table 2]. When vital signs are scheduled for the same time as a blood sample, the vital signs will be taken before the blood sample.

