6.5.1 Adverse Events

TEAE is defined as an AE observed after starting administration of the study drug through 30 days after EOT. The number and percentage of subjects with treatment-emergent AEs, serious adverse events (SAEs), AEs leading to withdrawal of treatment, and AEs related to study drug will be summarized by MedDRA system organ class, MedDRA High Level term, and MedDRA preferred term for overall subjects and by subjects in each age cohort. The number and percentage of AEs by severity will also be summarized. All AEs will be listed.

A study drug-related TEAE is defined as any TEAE with a causal relationship of YES by the investigator. The incidence of treatment emergent AEs will be summarized by relationship to study drug and severity for all subjects and by each age cohort. The protocol defines how Treatment Emergent AEs are determined. Although all AEs are collected, the summary Table will be based on the TEAEs.

Clinically significant out-of-range laboratory findings are to be determined and documented by the investigator/subinvestigator who is a qualified physician. Clinically significant changes will be recorded as AEs.

An overview table will include the following:

- Number of TEAEs,
- Number and percentage of subjects with TEAEs,
- Number of drug related TEAEs,
- Number and percentage of subjects with drug related TEAEs,
- Number of serious TEAEs,
- Number and percentage of subjects with serious TEAEs,
- Number of serious drug related TEAEs,
- Number and percentage of subjects with serious drug related TEAEs,
- Number of TEAEs leading to permanent discontinuation of study drug,
- Number and percentage of subjects with TEAEs leading to permanent discontinuation of study drug, and
- Number of deaths.

The number and percentage of subjects with TEAEs, as classified by SOC, High Level Term (HLT), and PT will be summarized. Summaries will be provided for the following:

- TEAEs

- drug related TEAEs,
- serious TEAEs,
- drug related serious TEAEs,
- TEAEs leading to permanent discontinuation of study drug,
- drug related TEAEs leading to permanent discontinuation of study drug,

The number and percentage of subjects with TEAEs, as classified by SOC and PT will be summarized by time interval. For each adverse event in a particular interval, a subject will be counted if there is an onset of a treatment-emergent adverse event regardless of onset in other intervals.

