6.5.4 Vital Signs

Descriptive statistics will be used to summarize vital sign results and changes from baseline for subjects in the SAF by treatment day from day 1 to day 84 (or EOT).

Vital signs data will be displayed in listings.

The baseline visit (screening predose period day -5 to 5) is the last non-missing measurement value taken prior to initial study drug administration. Post baseline visits will include vital signs measured prior to and again approximately 1 hour after the end of each infusion.

Vital signs (systolic blood pressure, diastolic blood pressure, pulse rate, respiratory rate and temperature) will be summarized using mean, standard deviation, minimum, maximum and median by Treatment Visit. Within subject change in vital sign values between visits will be summarized from baseline on.

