6.9 Analysis Windows

AEs and Vital signs will be summarized using Analysis Windows as below:

| Analysis Visits | Analysis Windows |
|------------------------|---|
| Baseline | Day(s) <=1 up to initiation of first dose |
| Day 2 | Day 2 |
| Day 3 | Day 3 |
| Day 7 | Day 5 to 9 |
| Day 14 | Day 12 to 16 |
| Day 21 | Days 19 to 23 |
| Day 28 | Days 26 to 30 |
| Day 35 | Days 33 to 37 |
| Day 42 | Days 40 to 44 |
| Day 49 | Days 47 to 51 |
| Day 56 | Days 54 to 58 |
| Day 63 | Day 61 to 65 |
| Day 70 | Days 68 to 72 |
| Day 77 | Days 75 to 79 |

Cont.

| | |
|----------------------|-----------------|
| Day 84 | Days 80 to 91 |
| Day 110 | Days 103 to 117 |
| Day 140 | Days 133 to 147 |
| Day 85 ¹ | Days 81 to 100 |
| Day 115 ¹ | Days 101 to 130 |
| Day 145 ¹ | Days 143 to 147 |
| Day 210 ¹ | Days 203 to 217 |
| Day 240 ¹ | Days 233 to 247 |

¹Applies to IM and IA/IM subjects.

See Appendix 1 for details of parameters for visit windows.

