9 APPENDICES

9.1 Appendix 1 Visit Windows

The value used is that which is closest to the defined assessment day and also within visit day windows. If two values are equally close, the latter is used in the analysis.

All the assessments will be allocated to electronic Case Report Form (eCRF) visit based on the table below.

Visit Windows

| Protocol visit | Target day | Visit window | Visit number |
|------------------------|------------|--------------------------------------|--------------------|
| Screening and Baseline | ≤D1 | D-5 to D1 | Pre dose period |
| V1 (Day1) | D1 | D1 | Visit 1 |
| V2 | D2 | D2 | Visit 2 |
| V3 | D3 | D3 | Visit 3 |
| V4 | D7 | D5 to D9 | Visit 4 |
| V5 | D14 | D12 to D16 | Visit 5 |
| V6 | D21 | D19 to D23 | Visit 6 |
| V7 | D28 | D26 to D30 | Visit 7 |
| V8 | D35 | D33 to D37 | Visit 8 |
| V9 | D42 | D40 to D44 | Visit 9 |
| V10 | D49 | D47 to D51 | Visit 10 |
| V11 | D56 | D54 to D58 | Visit 11 |
| V12 | D63 | D61 to D65 | Visit 12 |
| V13 | D70 | D68 to D72 | Visit 13 |
| V14 | D77 | D75 to D79 | Visit 14 |
| V15 | D84 | IA D77 to D91 or IM D82 to D86 | Visit 15 IA EOT |
| IA EOS | D110 | D103 to D117 | IA Follow-up |
| IA EOS | D140 | D133 to D147 | IA Follow-up |
| V16 | D115 | D113 to D117 | IM Visit 16 |
| V17 | D145 | D143 to D1146 | IM Visit 17 |
| V18 | D180 | D173 to D187 | IM Visit 18 EOT |

| | | | |
|--------|----------------------------|--------------|--------------|
| IM EOS | D210 (or 30 day EOS) | D203 to D217 | IM Follow-up |
| IM EOS | D240 (or 60 day EOS) | D233 to D247 | IM Follow-up |

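### The SAP's same-day averaging rule merges pre- and post-infusion vital signs, and its AE and vital-sign windows leave 22 of days 1–84 wholly or partly uncovered and conflict with Appendix 1

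*SAP*

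**What the plan says.** **Collection.** Protocol 5.4.1 states that vital signs "are to be measured within 1 hour before the start and approximately 1 hour after the end of each infusion on dosing days", with nothing extra on oral dosing days. SAP 6.5.4 places both readings in the same visit: "Post baseline visits will include vital signs measured prior to and again approximately 1 hour after the end of each infusion". It then summarises vital signs and their change from baseline by Treatment Visit, without naming a pre- or post-infusion time point.

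**Same-day rule.** The last paragraph of SAP 6.9.1 picks the observation nearest the scheduled day and then adds: "If more than one observation is made on the same day, an average value if continuous" is taken, while categorical data keep the worst value. No exception is stated for planned repeat readings.

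**Windows.** SAP 6.9 opens with "AEs and Vital signs will be summarized using Analysis Windows as below". Its Baseline row is "Day(s) <=1 up to initiation of first dose" and the next row is Day 2. SAP 6.9.1 adds for AEs: "The imputed dates will be used to allocate the concomitant medication and AEs to Treatment Visit". SAP 6.5.1 plans a table of TEAEs "as classified by SOC and PT will be summarized by time interval" but does not define the interval.

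**Second window table.** SAP 6.9 refers the reader to Appendix 1, which has its own table and says: "All the assessments will be allocated to electronic Case Report Form (eCRF) visit based on the table below".

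**The concern.** A paired reading around each infusion lets the analyst see what the infusion did. Protocol 1.2 names infusion-related reactions among the important drug-related events of the earlier pediatric study, and Protocol 6.1 lists hypotension first among the signs of a systemic reaction. Averaging the pair before summarising pulls the post-infusion value back toward the pre-infusion one. The tabulated minimum and maximum then become extremes of averages rather than of readings.

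The windows raise a separate problem. Visit windows with gaps suit scheduled measurements, but AE onsets follow no schedule. An onset on an uncovered day has no visit to go to. The first day of exposure is one such day, and SAP 6.9.1 also assigns AEs with a wholly missing onset date to the date of first dose. With two window tables that disagree, two programmers could both follow the SAP and produce different outputs.

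**Working it through.** The plan states no figure of its own on this point, so the check is to apply its rules.

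**1. Averaging.** Both readings around an infusion normally share a study day, so they are equally distant from the scheduled day and the averaging rule applies. Assume every other reading that day stays at its reference value and a post-infusion reading changes by d.

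- One infusion, two readings: (0 + d)/2 = d/2, or 50% of the change. Falls of 10, 20 and 30 mmHg would be analysed as 5, 10 and 15.
- Loading Day 2 with three infusions and six readings, one infusion reacting: d/6, or 17%.
- Same day, all three reacting equally: 3d/6 = d/2, or 50%.

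**2. SAP 6.9, days 1–84.** The post-baseline windows are 2, 3, 5–9, 12–16, 19–23, 26–30, 33–37, 40–44, 47–51, 54–58, 61–65, 68–72, 75–79 and 80–91. What is left:

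- Day 1 after the first dose, and day 4: 2 days
- 10–11, 17–18, 24–25, 31–32, 38–39, 45–46, 52–53, 59–60, 66–67, 73–74: 10 × 2 = 20 days

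Total 22, and 22/84 = 26.2%. Of these, 21 are wholly uncovered; Day 1 is covered only before dosing.

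**3. SAP 6.9, IM subjects, days 1–210.** The footnoted rows add 81–100, 101–130, 143–147 and 203–217.

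- If the Day 110 and Day 140 rows are for IA only, as Appendix 1 labels them: 22 + 12 (days 131–142) + 55 (days 148–202) = 89, and 89/210 = 42.4%.
- If those rows (103–117 and 133–147) also apply to IM: 22 + 2 (days 131–132) + 55 = 79, and 79/210 = 37.6%. On this reading days 103–117 and 143–147 each fall in two windows.
- On either reading, days 81–91 fall in both the Day 84 window (80–91) and the Day 85 window (81–100).

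**4. SAP 6.9 against Appendix 1.**

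| Visit | SAP 6.9 | Appendix 1 |
|---|---|---|
| Day 1 post-dose | no row | Day 1 |
| Day 84 | 80–91 | 77–91 (IA) or 82–86 (IM) |
| Day 85 (IM) | 81–100 | no row |
| Day 115 (IM) | 101–130 | 113–117 |
| Day 180 (IM) | no row | 173–187 |

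**5. Does Appendix 1 close the gaps?** Its Day 1 row removes one uncovered day: 22 − 1 = 21 of days 1–84 for IA (25.0%). For IM the narrower Day 84 window also drops days 80–81: 21 + 2 = 23 (27.4%). Its IA Day 84 window overlaps the Day 77 window (75–79) on days 77–79.

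**The case against.** **Pooling is inferred.** No sentence says outright that pre- and post-infusion readings are pooled. The averaging rule is general, and SAP 6.1 leaves table formats to separate TLF specifications that might split the time points. That is fair as far as it goes, but the SAP text taken alone gives one result, and a table specification should not have to override it.

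**The diluted quantity is not a planned estimate.** SAP 6.5.4 plans change from baseline by visit, not a paired post-minus-pre change, and infusion reactions are also reported as AEs. It is true that detecting a reaction does not rest on vital-sign means. The planned change from baseline is still blunted by the same averaging. The d/6 case also needs all three loading infusions and their readings to fall on one study day.

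**The gap counts overstate the effect on visits.** The two-day windows up to Day 77 match the visit windows in Protocol Table 1, so vital signs taken on schedule are not lost. SAP 6.5.4 starts its vital-sign summaries at Day 1 and Appendix 1 has a Day 1 row, so the Day 1 gap matters mainly for AEs. This stands.

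**The IM count depends on reading.** The Day 110 and Day 140 rows carry no footnote in SAP 6.9, so the literal count is 79 rather than 89. Both counts are given above; the literal reading brings the extra overlaps shown there.

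**Appendix 1 may simply be the detail behind 6.9.** SAP 6.9 does point to it. But the two tables give different limits for the same visits, so one cannot be the detail of the other.

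**The link from the 6.5.1 time interval to the 6.9 windows is an inference.** Agreed. What does not depend on it is the statement in SAP 6.9 that AEs are summarised in these windows.

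**Conclusion.** The concern holds. Read together, SAP 6.5.4 and 6.9.1 merge pre- and post-infusion readings, so a post-infusion change is shown at half size on a one-infusion day and at between one sixth and one half on a three-infusion day, assuming the other readings are unchanged and the reacting infusions change equally. Neither window table gives a complete allocation of AE onsets, and the two disagree on which days belong to the visits tabulated above.

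The consequence is bounded. Oral dosing days are unaffected. The overall, drug-related, serious and discontinuation TEAE tables need no windows, and all AEs and vital signs are listed. What suffers is the by-visit vital-sign summary for subjects on intravenous dosing and any AE table built on the windows. Safety is the first-listed objective and only about 30 subjects are planned, so these summaries should be right before the data are tabulated.

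**What to change.** 1. In SAP 6.9.1, exempt infusion vital signs from same-day averaging. In SAP 6.5.4, summarise pre- and post-infusion values as separate time points, and add the paired post-minus-pre change and the worst post-infusion value.
2. In SAP 6.5.1, define the time intervals for AEs as contiguous and non-overlapping, starting on Day 1 after the first dose, with cut-points chosen by the sponsor. Remove AEs from the scope of the visit windows in 6.9 and align the allocation sentence in 6.9.1.
3. Replace the tables in SAP 6.9 and Appendix 1 with one reconciled, non-overlapping visit-window table that includes Day 1 post-dose and Day 180 and states which rows apply to IA, IM and mixed infection.

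The cost is SAP wording and a few extra table rows. All the data are already collected.
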